6.1 Screening/Baseline Visit

- Informed Consent Discussion

- Inclusion/Exclusion criteria assessment
- Collection of demographics, significant medical history, and lymphedema history
- Urine pregnancy test (as applicable)
- Weight (kg) and height (cm)
- Skin assessment
- Limb circumference
- Photographs (Leg)
- Prescribed care and treatment protocol
- Medication review
- QoL Questionnaires
 - SF-36
 - LYMQOL
- Subject Diary (dispense)

6.2 Week 0/Training

- The subject will receive the Flexitouch system or Flexitouch Plus and be instructed on use from a Tactile Medical trainer. Device treatment will commence following the visit from the trainer.

6.3 Weeks 1 (+7 days), 18, 32, & 40 (± 14 days) Follow-up Phone Calls

- Prescribed care and treatment protocol
- Medication review
- Flexitouch compliance assessment
- Complication, adverse event, and device observation assessment

6.4 Weeks 4, 8, 12 (± 7 days), 24, and 52 (± 14 days) In-Clinic Follow-Up Visit(s)

- Weight (kg)
- Skin assessment
- Limb circumference
- Photographs (Leg)
- Prescribed care and treatment protocol
- Medication review
- QoL Questionnaires (Weeks 12, 24, and 52 only)
 - LYMQOL
 - SF-36
- Subject diary collection
- Flexitouch compliance assessment
- Complication, adverse event, and device observation assessment

7.0 Study Procedures

7.1 Informed Consent

Signed consent for participation in this study will be obtained prior to any research procedures. All study participants are required to sign an Institutional Review Board

(IRB) approved informed consent document that outlines the purpose of the study, requirements for participation, risks and benefits to participation, and subject's rights. Adequate time will be given for patients to read the consent form, to confirm their comprehension, and to decide on consent. Comprehension and capacity for consent will be assessed by the research staff.

The study staff will ensure that a valid consent is documented and placed in the patient's medical chart. A signed copy will be given to the subject/authorized representative and a copy will be maintained in the study file.

7.2 Demographics & Medical History

Demographics will be collected at baseline including the date of birth, ethnicity, race, gender, and employment status.

If the subject is female and of childbearing potential, a urine pregnancy test will be performed to ensure the subject is not pregnant. Per exclusion criterion 11, if a subject is pregnant or a women of childbearing potential not on contraception, they will be excluded from the study.

Significant medical history and lymphedema history will be collected at baseline including number of lymphedema and venous related visits that required health care utilization (HCU) (includes clinic visits, hospitalization, walk-in clinic/urgent care, and ER visits).

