**Assessment of Quality of Life Changes on Lower Extremity
Lymphedema Patients using an Advanced Pneumatic
Compression Device at Home.**

Protocol# 5010

**03 July 2019
Protocol Version 3.1**

Investigator Signature

Protocol Title: Assessment of Quality of Life Changes on Lower Extremity Lymphedema Patients using a Pneumatic Compression Device at Home.

Protocol Number: 5010

Date: 03 July 2019, Version 3.1

I confirm that I have read this protocol. I will comply with the protocol and the principles of Good Clinical Practices (GCP), institutional research policies and procedures and other appropriate regulatory requirements.

Site Principal Investigator Name (Print)

Site Principal Investigator Signature

Date

SYNOPSIS

Title of Study	Assessment of Quality of Life Changes on Lower Extremity Lymphedema Patients using an Advanced Pneumatic Compression Device at Home.
Protocol Date	3 July 2019
Protocol Version	3.1
Name of Sponsor	Tactile Medical™
Device	Flexitouch® system or Flexitouch® Plus
Primary Endpoint	Quality of life (QoL), lymphedema symptoms, lymphedema and venous related complication rate, lymphedema and venous related unscheduled visits
Secondary Endpoint	Limb circumference changes, Flexitouch compliance, skin changes, QoL
METHODOLOGY	
Study Design	Multi-center, single arm, observational clinical trial
Treatments	Subjects will be instructed to use the Flexitouch system or Flexitouch Plus as prescribed and will be followed for 52 weeks. The subjects will be seen in clinic 4, 8, 12, 24 and 52 weeks after completion of device training. The subject will also have phone call follow-ups at 1, 18, 32 and 40 weeks after device training.
Treatment Duration	As prescribed
SUBJECT POPULATION	
Number Planned	300
Inclusion Criteria	
 1) Age 18 or older 2) Diagnosis of primary or secondary, unilateral or bilateral, LE lymphedema 3) Ability and willingness to participate in all aspects of the study including following prescribed care 4) Ability to provide informed consent 5) Must have a prescription for the Flexitouch (Flexitouch system or Flexitouch Plus)

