5.1 Study Endpoints

5.1.1 Primary Endpoints

The following primary endpoints for this study will compare changes after 12 weeks of treatment to baseline for the following parameters:

- QoL
- Lymphedema symptoms

In addition, the number of occurrences after 52 weeks of treatment will be compared to the number of occurrences in the year preceding treatment for the following variable:

- Lymphedema and venous related health care utilization

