7.11 Lymphedema and Venous Related HCU, Device-Related Adverse Events, & Device Observations

At each phone call and clinic follow-up visit, assessment of lymphedema and venous related HCU, device-related adverse events, and device observations will occur and be recorded in Clindex, per the following definitions.

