7.11.1 Lymphedema and Venous Related HCU

Lymphedema and venous related visits that required HCU (includes clinic visits, hospitalization, walk-in clinic/urgent care, and ER visits).

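### The primary HCU comparison sets one retrospective baseline count, of unstated source and dates, against counts built up over nine follow-up contacts, so a change in ascertainment can create or hide a change in visits

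*Combined protocol and SAP*

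**What the plan says.** Section 5.1.1 lists HCU as a primary endpoint and states that "the number of occurrences after 52 weeks of treatment will be compared to the number of occurrences in the year preceding treatment".

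The two sides of that comparison are collected as follows.

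- **Year before treatment.** Section 7.2 states that "lymphedema history will be collected at baseline including number of lymphedema and venous related visits that required health care utilization". It does not say whether the count comes from the subject, the chart or another record, gives no look-back dates, and describes no verification. In the schedule (7.13) the HCU row is blank at baseline; the count can only sit under medical history, whose footnote covers lymphedema history.
- **52 weeks on treatment.** Section 7.11 states: "At each phone call and clinic follow-up visit, assessment of lymphedema and venous related HCU, device-related adverse events, and device observations will occur". Sections 6.3, 6.4 and 7.13 place these contacts at Weeks 1, 18, 32 and 40 (phone) and Weeks 4, 8, 12, 24 and 52 (clinic).

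The design is single arm (5.0). Section 13.1 names no analysis for HCU, no adjustment for differing ascertainment and no sensitivity analysis.

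**The concern.** A before/after comparison of counts is interpretable only if visits are found with about the same completeness in both periods. Here one period is covered by a single look back and the other by repeated questioning. If completeness differs, the difference passes straight into the estimated change.

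A control group going through the same switch would let this cancel, but there is none. Nor does a larger sample help: it narrows the interval around a biased ratio. At stake is whether a reported fall, rise or absence of change in a primary endpoint can be read as a statement about visits at all.

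**Working it through.** **No figure of the plan's to reproduce.** The documents give no HCU rate, dispersion, test, significance level or power. The 300 subjects are described as a convenience sample (13.2).

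**Number and spacing of contacts (6.3, 6.4, 7.13).** 4 phone + 5 clinic = 9. Gaps from Day 0, in weeks: 1, 3, 4, 4, 6, 6, 8, 8, 12. They sum to 52, so the mean is 52 / 9 = 5.8 weeks. The baseline count looks back over a year in one step.

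**Effect of unequal capture.** Let B be the recorded baseline count, P the cumulative prospective count, θ the true on-treatment/prior ratio, and c0 and c1 the fractions of true visits recorded at baseline and in follow-up. Then

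P / B = θ × c1 / c0.

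The documents give neither c0 nor c1, so the ranges below are assumptions. With no true change (θ = 1):

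| Baseline capture c0 | c1 = 0.8 | c1 = 0.9 | c1 = 1.0 |
|---|---|---|---|
| 0.6 | 1.33 | 1.50 | 1.67 |
| 0.7 | 1.14 | 1.29 | 1.43 |
| 0.8 | 1.00 | 1.125 | 1.25 |
| 0.9 | 0.89 | 1.00 | 1.11 |
| 1.0 | 0.80 | 0.90 | 1.00 |

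The extremes are 0.8 / 1.0 = 0.80 and 1.0 / 0.6 = 1.67. Over-reporting at baseline would act as c0 above 1 and could take the ratio below 0.80.

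**Chance of a misleading test result.** This is a simulation with further assumptions: 300 subjects, paired Poisson counts with a shared gamma frailty of shape 1, a paired z-test at two-sided 0.05, 1,500 runs, and true mean rates of 0.5, 1, 2 and 4 visits per year.

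| True ratio | c0 | c1 | Observed ratio | Result counted | Share of runs at 0.5 / 1 / 2 / 4 visits per year |
|---|---|---|---|---|---|
| 1.0 | 0.90 | 0.90 | 1.00 | significant, either way | about 4-6% throughout |
| 1.0 | 0.80 | 0.95 | 1.19 | false increase | 28 / 50 / 80 / 97% |
| 1.0 | 0.95 | 0.80 | 0.84 | false decrease | 26 / 49 / 78 / 98% |
| 0.8 | 0.90 | 0.90 | 0.80 | true decrease found | 39 / 68 / 94 / >99% |
| 0.8 | 0.75 | 0.95 | 1.01 | true decrease found | about 1-3% throughout |

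The last ratio is 0.8 × 0.95 / 0.75 = 1.01: the benefit disappears.

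**What a repeated item would add.** Let W be the count from the identical item at Week 52, with capture c0′. Then W / P = c0′ / c1, which the trial can observe within subjects, and W / B = θ × c0′ / c0. If the item captures equally well on both occasions (c0′ = c0), W / B recovers θ and W / P estimates the differential capture.

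**The case against.** In a single-arm post-market cohort, the year before enrollment has to be collected retrospectively. Sections 7.2 and 7.11.1 use the same definition and visit types, so what is shown to differ is the frequency of asking, not the definition. Section 5.1.1 does set the comparison period as the preceding year, so the silence of 7.2 is partly a drafting gap. All of this stands. It leaves the source, the exact dates and the difference in ascertainment unaddressed.

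A reader might infer that the baseline count is the subject's unaided 12-month recall. The documents do not say so. Section 11.2 lists clinic charts among source documents and 11.5 requires complete medical records for each subject, so a chart-based count is compatible with the text. It could still differ in completeness from questioning at nine contacts.

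A reader might also infer that frequent asking must find more visits, so that the bias hides a benefit. Nothing in the documents establishes that. Under-capture at baseline would hide a reduction; over-reporting at baseline or under-capture in follow-up would create one.

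Finally, it is tempting to make a Week 52 item the primary measure. By then the subject has been asked about HCU at eight earlier contacts, so the answer may be primed in a way the baseline answer was not. The item is also missing for anyone who leaves early under 5.2.3 or 7.10, for whom the prospective contacts still hold a partial count. These objections are sound, and they confine the item to a supporting role.

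**Conclusion.** The concern holds as a difference in ascertainment of unknown direction. Carried out as written, the primary HCU comparison mixes true change with a change in how visits are found, and the plan contains nothing to separate the two. Under assumed capture of 0.6 to 1.0 at baseline and 0.8 to 1.0 in follow-up, the observed ratio is 0.80 to 1.67 with no true change. The capture ranges, and the visit rates, frailty and test behind the simulated percentages, are assumptions and not trial data. What the documents themselves establish is the single baseline count without source or dates, the nine follow-up contacts, the lack of a control group and the lack of any planned adjustment. This should be corrected. It does not show that the endpoint is biased in favor of the device or against it.

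**What to change.** 1. In 7.2, define the baseline HCU item as the 12 months before Day 0, by visit type (clinic, walk-in/urgent care, ER, hospitalization), from a stated source. The baseline visit precedes Day 0 by an interval that is not fixed, so state how the days in between are filled in; the Week 1 call already asks about HCU.
2. At Week 52, ask the identical item, from the same source, about the 12 months since Day 0.
3. Keep the contact-by-contact prospective count. Pre-specify the matched comparison (Week 52 item against baseline item) beside the prospective comparison.
4. Use the within-subject difference between the Week 52 item and the cumulative prospective count to estimate differential capture.
5. State in section 13.1 that no HCU change will be claimed unless both comparisons agree in direction.

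The cost is one added case report form item at an existing visit and tighter wording at baseline, with no new procedure. The limits are possible priming at Week 52 and availability only for subjects who reach that visit, so the item supports the prospective count and does not replace it. Both comparisons share the same baseline count and neither supplies a control group, so agreement is a safeguard and not proof of a device effect.

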7.3 Vital Signs

At the screening/baseline visit, height (cm) and weight (kg) will be collected. Weight will be collected at all other clinic visit follow-ups.

7.4 Skin Assessment

Skin will be assessed at each clinic visit by fibrosis grading, assessment of skin changes, and staging of lymphedema using ISL guidelines.

7.4.1 Fibrosis Grading

Fibrosis grading will use the following guidelines:

- Grade 0: Latent with no evident fibrosis
- Grade 1: Soft tissues responds only minimally or moderately to elevation (raising the limb) or compression; texture is moderately firm or spongy
- Grade 2: Marked increase in density and firmness; "tethering" of skin (changes in texture that makes skin look as it is being pulled from within)
- Grade 3: Very marked density and firmness with evident tethering

7.4.2 Assessment of Skin Changes

The assessment of skin changes will be done by recording the presence or absence of:

- Hyperpigmentation, Discoloration
- Hyperkeratosis

- Dermatitis, Eczema
- Ulceration, Blisters
- Positive Stemmer Sign
- Squaring of Toes
- Deep Creasing at Flexion Points
- Papillomas
- Puffy Forefoot/Swelling on Dorsum
- Increase of Fat or Muscle Bulk
- Lymphorrhea, Weeping Edema

7.4.3 Lymphedema Staging

The staging of lymphedema will follow ISL guidelines as shown in Table 3.

Table 3. ISL Staging Guidelines

Stage	Description
Stage 0	Latent with no clinical signs (no evident swelling).
Stage 1	Soft swelling (pitting) that resolves with elevation.
Stage 2	Spongy swelling (pitting and non-pitting) that does not resolve with elevation; fibrosis may or may not be present.
Stage 3	Symptoms of lymphostatic elephantitis where pitting is absent and tropic skin changes develop; extensive fibrotic swelling, blistering, ulceration, lymphorrhea, papilloma, and/or recurrent infections may be present.

7.5 Limb Circumference Measurements

Limb circumference measures will be taken at each in-clinic visit for both legs. The circumference measurements will be completed by research personnel with documented training showing the individual was able to independently and accurately conduct the measurements. Measurements will be collected using a Gulick II tape measure provided by Tactile Medical. In addition, if possible, the same clinician will be asked to take the measurements for each subject serially.

Standard limb measurement will involve taking two circumference measurements at 18 cm from the floor and 10 cm above the popliteal.

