5.1.2 Secondary Endpoints

The secondary endpoints for this study will compare changes after 12 and 52 weeks of treatment to baseline for the following:

- Limb circumference
- Skin evaluation

In addition, changes after 24 and 52 weeks of treatment to baseline for the following parameter:

- QoL

To assess Flexitouch compliance, subjects will be categorized as noncompliant, partially compliant, or compliant (Table 1). Primary and secondary outcomes will then be compared across the defined compliance categories.

Table 1. Compliance Category Definitions

Compliance Category	Definition
Noncompliant	Prescribed care followed an average of 0-2 days per week.
Partially Compliance	Prescribed care followed an average of 3-4 days per week.
Compliant	Prescribed care followed an average of 5-7 days per week.

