5.2.2 Exclusion Criteria

1. Diagnosis of active or recurrent cancer, or less than 3 months at the time of initial evaluation from the completion of chemotherapy, radiation therapy or primary surgery for the treatment of cancer.
2. Active skin or limb infection/inflammatory disease (acute cellulitis, or other uncontrolled skin or untreated inflammatory skin disease)
3. Acute thrombophlebitis (in last 2 months)
4. Pulmonary embolism within the previous 6 months
5. Deep Vein Thrombosis (DVT) within the previous 3 months
6. Severe peripheral artery disease (critical limb ischemia including ischemic rest pain, arterial wounds, or gangrene)
7. Pulmonary edema
8. Heart failure (acute pulmonary edema, decompensated acute heart failure)
9. Patients with poorly controlled asthma
10. Previous use of the study PCD

11. Currently using multi-layer bandaging (MLB) unless bandages can be removed for limb circumference measurements
12. Pregnant women or women of childbearing potential not on contraception
13. Any condition where increased venous and lymphatic return is undesirable
14. Currently participating in another medical device or drug clinical trial
15. Signs of noncompliance at the week 4 visit, including: using the device less than 3 times per week and/or not attending the scheduled visit

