7.5.1 Mark Anatomical Sites

Using a pen or skin marker, with the subject standing upright and bearing weight on the limb being measured, mark the subject at the lateral aspect of the leg 18 cm from the floor (see Figure 2), at the popliteal, and 10 cm from the popliteal (Figure 3).

[figure not shown]

Figure 2. Site A is 18 cm from the floor on lateral aspect of the leg.

[figure not shown]

Figure 3. Site B is the popliteal and Site C is 10 cm above the popliteal.

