7.5.2 Circumference Measurements

After marking the anatomical sites, measure and record the circumference, in cm, at sites A (see Figure 4) and C (see Figure 5). The tape measure must be placed precisely over (covering) the skin marking. Adjust the tension of the tape measure so that one red ball is visible in the tension indicator and record the circumference measurement.

Figure 4. Site A circumference measurement.

[figure not shown]

Figure 5. Site C circumference measurement.

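### Limb circumference is measured without fixing or recording time since the last device session, garment or bandage, so any short-lived post-session reduction cannot be separated from the 12- and 52-week change

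*Combined protocol and SAP*

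**What the plan says.** Section 5.1.2 lists limb circumference as a secondary endpoint: "The secondary endpoints for this study will compare changes after 12 and 52 weeks of treatment to baseline for the following". The same section plans to compare outcomes across three compliance categories.

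Section 7.5 says when the measurement is made: "Limb circumference measures will be taken at each in-clinic visit for both legs". Sections 7.5 to 7.5.2 then control several sources of error:

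- Assessor: trained, and "if possible, the same clinician will be asked to take the measurements for each subject serially".
- Posture for marking the sites: "with the subject standing upright and bearing weight on the limb being measured". Section 7.5.2 does not repeat this for the measurement itself.
- Tape: "Adjust the tension of the tape measure so that one red ball is visible in the tension indicator and record the circumference measurement".

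These sections set no time of day, no interval since device use and no interval since compression was removed, and none of these is recorded. Sections 6.4 and 7.13 add only visit windows in days. Section 6.0 lets a site offer a home visit without saying anything about device use beforehand. Section 5.3 leaves the device schedule to the prescription and treats garments as routine care; neither is tied to visits.

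On bandaging, Section 5.2.2 (criterion 11) excludes a patient who is "Currently using multi-layer bandaging (MLB) unless bandages can be removed for limb circumference measurements". It does not say how long the bandage must be off before the tape goes on.

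**The concern.** The endpoint is a within-subject difference, so it is sound only if the limb is in a comparable state at both measurements. For recent device use it cannot be. Criterion 10 in Section 5.2.2 excludes earlier users of the study device, and Section 7.12 places training after the baseline visit. No baseline limb has had a session, whereas a follow-up limb may have had one hours before. If a session empties the limb for a while, the effect enters one side of the difference only, and a single-arm study has no comparison group from which to subtract it.

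The compliance comparison is exposed as well. Frequent users are more likely to have had a recent session when measured, so a transient effect alone could look like a dose-response.

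**Working it through.** The plan gives no figure on this point. The planned enrolment of up to 300 (Section 13.2) is a convenience sample with no alpha, power, effect size or SD, so there is nothing to reproduce. The first two steps set the sections side by side; the rest is arithmetic on stated assumptions.

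**1. When each source of compression can act**

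- Study device: not at baseline (criterion 10; Section 7.12); possible at every follow-up visit. One-sided.
- Compression garments: possible at both times (Section 5.3). No built-in direction.
- Multi-layer bandaging: possible at baseline (criterion 11) and at follow-up. It biases the change only where a subject's bandaging status differs between the two visits.

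**2. Whether the data could repair this later**

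- The compliance assessment (Section 7.10) counts days of use over the preceding week, with no hours.
- The diary (Section 7.10, Appendix C) is a daily tick. It does not show whether a session on the visit day came before or after the measurement.
- The device log (Section 7.10) is optional and covers only Flexitouch Plus units.
- Current treatment (Section 7.7) is recorded at each visit, so bandaging at baseline should be identifiable. Time since removal is not.

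**3. Possible size of device carry-over (assumptions)**

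Mean spurious reduction = share of follow-up visits soon after a session × carry-over. Assume a 40 cm circumference lowered by 1 to 2% (0.4 to 0.8 cm) and a share of 25 to 75%.

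- Low: 0.25 × 0.4 = 0.10 cm
- High: 0.75 × 0.8 = 0.60 cm

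**4. Scale against precision (assumptions)**

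Take one change score per subject, n = 300, two-sided alpha 0.05 and no lasting change. SE = SD/√n, and the probability of declaring a change is Φ(b/SE − 1.96) + Φ(−b/SE − 1.96), where b is the mean carry-over. For SD 2.5 cm, SE = 2.5/√300 = 0.144 cm.

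| SD of change | 95% half-width | b = 0.25 cm | b = 0.5 cm |
|---|---|---|---|
| 1.5 cm | 0.17 cm | 0.82 | 1.00 |
| 2.5 cm | 0.28 cm | 0.41 | 0.93 |
| 4.0 cm | 0.45 cm | 0.19 | 0.58 |

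With n = 200 and b = 0.5 cm the probabilities are 1.00, 0.81 and 0.42.

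**5. Bandaging at baseline (assumptions)**

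Shift in the opposite direction = share bandaged at baseline × share r of those no longer bandaged at follow-up × amount by which baseline is too small. Assume 5 to 15% bandaged and a baseline 2 to 5% too small (0.8 to 2.0 cm).

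- r = 1: 0.05 × 0.8 = 0.04 cm to 0.15 × 2.0 = 0.30 cm
- r = 0.5: 0.02 to 0.15 cm
- r = 0: none

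**6. Net direction**

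Suppose half the follow-up visits carry 0.5 cm of device effect, and bandaged baselines are 1.0 cm too small with r = 1. At 10% bandaged the net apparent reduction is 0.5 × 0.5 − 0.1 × 1.0 = 0.15 cm. At 30% bandaged it is 0.25 − 0.30 = −0.05 cm. The sign depends on the mix.

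**7. Compliance categories (assumptions)**

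Table 1 defines the categories by days of prescribed care per week. Treat these as days of device use unrelated to the visit day, and take the midpoints: 6 days for compliant and 3.5 for partially compliant. The difference in the chance that the visit falls on a use day is (6 − 3.5)/7 = 0.36. If every such session preceded the visit, 0.4 to 0.8 cm of carry-over would give a gap of 0.14 to 0.29 cm between the categories. If half did, the gap would be 0.07 to 0.14 cm.

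**The case against.** The strongest reply is that the documents nowhere show that a session or garment shrinks the limb for hours. The nearest support is Stage 1 in Table 3 of Section 7.4.3, "Soft swelling (pitting) that resolves with elevation", which concerns elevation, not compression. The same table describes Stage 2 swelling as not resolving that way, and eligibility has no stage limit, so Stage 1 cannot stand for the cohort. This stands: carry-over and its size are assumptions.

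Second, this is a post-market observational study of treatment as prescribed, and limb size during ongoing use is a legitimate target. That is fair, but even then the result depends on when in the use cycle the limb was measured. The plan neither fixes nor records that.

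Third, day-level data already exist. They would largely identify pairs without same-day use, and bandaging at baseline. They cannot order session and measurement within a day, or give hours. The no-same-day subset is also selected on behaviour after baseline and would under-represent frequent users, so it can only be supportive.

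Fourth, patients who remain bandaged and are measured with the bandage off at both visits form comparable pairs. This stands, and is why step 5 carries the factor r.

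A reader might extend the point to all skin findings. The documents give limited support: Section 7.4.1 defines fibrosis grades 2 and 3 by density, firmness and tethering, not by fluid.

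**Conclusion.** The point holds as a gap in measurement and recording that leaves a one-sided bias possible. Device carry-over can enter only at follow-up, no control arm can remove it, and the planned data cannot reliably recover the missing hours. Any carry-over present is therefore inseparable from the 12- and 52-week change in circumference, and may differ between compliance categories.

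Under the stated assumptions the device part is 0.10 to 0.60 cm. The bandage part runs the other way, from zero to 0.30 cm depending on how many change status. None of these inputs comes from the documents.

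Two stronger readings should be resisted. One is that carry-over is being counted as lasting change and that benefit is overstated. The documents show neither its presence nor its amount, garments can act at both times, and the net sign can reverse (step 6). The other is that the main result is compromised. Section 5.1.1 names QoL, lymphedema symptoms and health care utilization as primary, and circumference is not among them. The point is worth correcting because the remedy is cheap and unrecorded hours cannot be reliably recovered, but its reach is limited to secondary analyses.

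**What to change.** In Section 7.5, for baseline and for every clinic or home visit:

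- Record clock time, hours since the last Flexitouch session (not applicable at baseline) and hours since removal of any garment or bandage.
- Schedule each subject's visits at a similar time of day where possible.
- Measure after the same short interval from garment or bandage removal at each visit, with the interval stated in the protocol.

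A few minutes of seated rest should not be relied on as a remedy for carry-over, because it would not remove an effect assumed to last hours.

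In Section 13.1, keep the planned 12- and 52-week comparison. Add a sensitivity analysis stratified by, or adjusted for, hours since the last session, and apply it to the compliance-category comparison too. Show pairs without same-day device use as supportive only, noting that the subset is self-selected. Report subjects bandaged at baseline separately, with their bandaging status at follow-up.

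The cost is a few extra form fields and some scheduling inconvenience. Prescribed treatment does not change.
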